3.4 Primary Effectiveness Endpoint

The primary effectiveness endpoint (PEE) is the proportion of LUX-Dx monitored Treatment Subjects with Treatment Success through the Day 360 Assessment. Treatment Success is defined as Persistent AF Acute Procedural Success AND Persistent AF Chronic Success.

3.4.1 Persistent AF Acute Procedural Success

Persistent AF Acute Procedural Success is defined as:

- The isolation of all attempted PVs as clinically assessed at the end of the procedure by entrance block performed with or without adenosine testing, AND
- The isolation of the left atrial PW as clinically assessed at the end of the procedure, performed with or without adenosine testing, via interrogation by multipolar diagnostic catheter or 3D electroanatomical mapping.

Both PWI and PVI must be achieved using only the FARAWAVE Catheter to be classified as a Persistent AF Acute Procedural Success. If the Investigator determined that subject welfare required intervention for an accessory pathway, AVNRT or spontaneously occurring treatment-emergent AFL or AT, ablation for these arrhythmias may be performed using any commercially available RF ablation catheter, and these permitted ablations do not constitute Persistent AF Acute Procedural Failure.

3.4.2 Persistent AF Chronic Success

Persistent AF Chronic Success is defined as freedom from any of the following through the Day 360 Assessment after the Blanking Period, excluding documented CTI-dependent AFL¹:

- a. **Arrhythmia:** Occurrence of any Detectable AF, AFL or AT
- b. **Re-ablation:** Any re-ablation for AF, AFL or AT
- c. **Cardioversion:** Any electrical cardioversion for AF, AFL or AT
- d. **AAD Use:** Use of a Non-Failed Class I / III AAD or amiodarone

Within the Blanking Period, recurrent arrhythmias can be managed with AADs, cardioversion or one re-ablation procedure with the FARAPULSE PFA System without constituting Persistent AF Chronic Failure. Titration of Class I/III antiarrhythmic medications are allowed during the Blanking Period. Subjects are allowed to remain on Class I/III antiarrhythmic medications at the historic maximum ineffective dose (prior to the ablation procedure) after the 90-day Blanking Period, except amiodarone. Subjects that undergo more than one re-ablation procedure within the Blanking Period will be classified as a Persistent AF Chronic Failure. Complete definitions of the endpoint terms (including Blanking Period, Detectable AF, AFL, or AT, Failed AAD and Non-Failed AAD), can be found in **Section 23.2**.

¹ Post-blanking CTI-dependent AFL or re-ablation or cardioversion for CTI-dependent AFL does not constitute Treatment Failure if the subject did not have a CTI ablation with the FARAPULSE PFA Catheter but will be a Treatment Failure if the subject did receive ablation with the FARAPULSE PFA Catheter.

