Treatment Success as defined in **Section 3.4** but counting subjects with any re-ablation for AF, AFL, or AT as Treatment Failures

- **Off Drug Treatment Success**

Treatment Success as defined in **Section 3.4** but counting subjects treated with any Class I / III AAD after Day 90 as Treatment Failures

- **Re-Ablation Rate**

Defined as the proportion of subjects who receive one or more re-ablations during study follow-up for AF, AFL, or AT, at any time during follow-up, and subdivided by re-ablation during Days 0 – 90 and by Days 91 and thereafter. CTI only re-ablation is excluded for subjects who did not receive CTI ablation with the FARAPPOINT catheter.

- **AF, AFL, and AT Burden**

Descriptive statistics on AF, AFL, and AT burden, as defined in Section 23.2 and assessed during the observation period from Day 91 to Day 360 Assessment. AF, AFL, and AT burden will also be calculated for the days from LUX-Dx activation to the Index/ Rescheduled Index Procedure (up to 30 days pre-procedure) and compared to the burden calculated from Day 91 to Day 360 Assessment. Additionally, AF, AFL, and AT burden statistics from Day 91 to Day 360

will be stratified by recurrence based on LUX-Dx detected AF, AFL, or AT using various episode duration thresholds.

- **Healthcare Utilization by AF, AFL, and AT Burden**

Healthcare utilization, defined by outcomes of all-cause hospitalization, cardioversion for AF, AFL, or AT recurrence outside of an ablation procedure, re-ablation for AF, AFL, or AT and unscheduled cardiovascular follow-up assessments, will be compared between subjects grouped by AF, AFL, and AT burden from Day 91 to Day 360 Assessment. Burden groups will include rates of 0%, 0-0.1%, 0.1-1%, 1-5%, 5-10%, and >10% AF, AFL, and AT burden.

- **Healthcare Utilization by AF, AFL, or AT Recurrence Duration**

Healthcare utilization, defined by outcomes of all-cause hospitalization, cardioversion for AF, AFL, or AT recurrence outside of an ablation procedure, re-ablation for AF, AFL, or AT and unscheduled cardiovascular follow-up assessments will be compared between subjects grouped by longest duration of AF, AFL, or AT captured by LUX-Dx (based on continuous monitoring) between Day 91 and Day 360 Assessment. Groups will include no recurrence and longest duration of 0-6 minutes, 6 minutes – 1 hour, 1-6 hours, 6-24 hours, and \geq 24 hours.

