Tachy Response	Less	Yellow Alert
AT Detection	On	Alert for Tachy Events –
AT Duration	4 hours at 110 bpm	On Red Alert

Any programming outside of these nominal parameters prior to a confirmed recurrence of Detectable AF, AT or AFL must be entered into the EDC and justification provided.

7.7 *Index Procedure / Rescheduled Index Procedure*

7.7.1 *Index Procedure / Rescheduled Index Procedure Data Collection*

Type of Assessment: In-person at investigational site
The performance of the Index Procedure / Rescheduled Index Procedure and the Pre-Discharge Assessment both require an in-person assessment. The Index Procedure / Rescheduled Index Procedure must be deferred if this is not possible.

Procedural data will be collected including but not limited to:

- The results of transesophageal echocardiography (TEE) or volumetric CT within 48 hours prior to procedure, or intracardiac echocardiography (ICE) prior to transseptal puncture, utilized for exclusion of LA thrombus.
- Pregnancy test (all women of childbearing potential if the baseline pregnancy test was obtained more than 30 days prior to the Index Procedure / Rescheduled Index Procedure)
- Documentation of PVI for each attempted vein, of PWI, and if performed, of CTI BDB
- Post-ablation electroanatomical maps, if performed with Rhythmia
- The functional status of both phrenic nerves will be assessed radiographically pre and post ablation.
- Method of sedation or anesthesia
- Whether adenosine was used to confirm PVI and / or PWI
- Whether a post-procedure cardioversion was performed
- Adverse events
- For the 3D mapping system: Manufacturer and model, when applicable
- 12-lead ECGs pre- and post-ablation
- Procedural times
- Ablation data

- Procedural anticoagulation data:
 - For subjects on a DOAC whether DOAC therapy was interrupted for procedure
 - For subjects on warfarin, a pre-ablation international normalized ratio (INR) value
 - Procedural heparin administration and timing
- Device deficiencies and malfunctions

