7.7.2.5 CTI Ablation

The following subjects will undergo CTI ablation with the FARAPoint PFA Catheter:

- Required: For subjects with a history of CTI-mediated (typical) AFL and
 - Who have not had a CTI ablation procedure, or
 - Who have had a CTI ablation procedure but have recurrent CTI conduction.
- Required: Subjects who manifest CTI-mediated AFL (spontaneous or induced) during the Index Procedure
- At Investigator discretion: Subject welfare indicates that CTI ablation should be performed.

CTI Ablation with the FARAPoint PFA Catheter will be performed according to the IFU documents and institutional practice. Per the FARAPoint Catheter IFU, no more than two energy applications should be delivered at any given catheter placement. Repeat placement of the FARAPoint Catheter at nearly identical locations should be avoided unless there is a clear clinical need for such placements.

The FARAWAVE Catheter is not allowed to complete any CTI lesion.

CTI ablation with the FARAPoint PFA Catheter must adhere to the following protocol requirements in order to mitigate the risk of coronary spasm during ablation application.

No ablations outside CTI with the FARAPoint PFA Catheter are allowed.

The following prophylactic workflow is required to be followed when CTI ablation is performed with the FARAPoint PFA Catheter:

- **Pre-Treatment (Required)**: Administer a three milligrams (3mg) nitroglycerin IV bolus via the FARADRIVE sheath (or other sheath with central access) approximately one minute prior to the first PFA application at the anterior position of the CTI line.
- **During Ablation (Required)**:

⁷ If anesthesia necessitates, a pre-discharge fluoroscopic sniff test or inspiration / expiration CXR may be acceptable. See **Section 7.8**.

- Depending upon procedure duration and patient condition, administer an additional 2mg IV bolus via the FARADRIVE sheath (or other sheath with central access) approximately two (2) minutes apart until the ablation is complete or a maximum total of 9mg IV of nitroglycerin has been administered.
- If bidirectional block (BDB) is assessed and not present and additional ablation lesions are required in the anterior aspect of the cavo-tricuspid isthmus line, Investigator discretion will determine whether to administer an additional 2-3 mg of nitroglycerin IV via the FARADRIVE sheath (or other sheath with central access) prior to re-ablation.

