7.14 Re-Ablation Procedures

7.14.1 Re-Ablation Procedure within the Blanking Period

For subjects undergoing a first re-ablation procedure within the Blanking Period for Detectable AF, AFL or AT, the procedure will be performed by the investigator under the procedures and data

requirements of **Section 7.7.1**, modified to assess and treat only those locations required, and including the pre- and post-procedure NIHSS.

The FARAPoint PFA Catheter will not be utilized for any re-ablation procedure. If repeat ablation is required for CTI-mediated flutter, any commercially available BSC RF catheter will be used. Such re-ablation using the methods and devices described in **Section 7.7.1** does not constitute a Treatment Failure.

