7.14.2 Other Re-Ablation Procedures

For a second re-ablation during the Blanking Period and for any re-ablation after the Blanking Period, any commercially available ablation catheter will be used for re-ablation.

The FARAPULSE Pulsed Field Ablation System is not permitted to be used for these procedures.

Such re-ablations constitute Treatment Failures, and therefore during such procedures other sites may be ablated at Investigator discretion.

The following data will be collected for these procedures:

- Adverse events
- During re-ablation procedures, a mapping procedure will be performed to characterize the reconnection status for each originally treated PV and the PW (if a left-sided re-ablation), and the CTI, to characterize lesion durability.
- Limited ablation data.

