Blanking Period	
An interval in which recurrent AF, AFL or AT, cardioversion or a first re-ablation do not constitute Treatment Failure beginning on Day 0 and running for 90 days thereafter.
 
 • The Blanking Period has no impact on the assessment of AEs. • For subjects with only an Index Procedure, the Blanking Period will be Day 0 to Day 90 inclusive. • For subjects who require a Rescheduled Index Procedure, the Blanking Period will be the Study Day of the Rescheduled Index Procedure (Day 0) plus 90 days inclusive • For subjects treated with a Non-Failed AAD during the Blanking Period, a Treatment Failure due to the use of that drug only occurs if there is continued use of that drug following the earlier of either the Day 90 visit or Day 104.
(Persistent AF) Chronic Success	Defined in Section 3.4.2.
Composite Serious Adverse Events	Composite Serious Adverse Events are defined in Section 3.3.
COVID-19 Related Disruptions	A disruption to any study procedure resulting directly or indirectly from the COVID 19 pandemic, including but not limited to subject illness, study site restrictions and limitations, shipping / manufacturing interruptions, significant changes in regulatory guidance and / or governmental restrictions on travel, association, and the prioritization of healthcare resources.
Dates	
 • Consent Date: The date a subject signs the ICF. • Exit Date: The date on which a subject's study participation ends. • Onset Date: The date on which a condition or AE begins. • Start Date: Day 0, the date of the Index Procedure or Rescheduled Index Procedure
Day (or Study Day)	A Day is an enumerated day of follow-up that begins on an Enrolled Subject's Start Date (Day 0).

Term	Definition

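### Appendix A (Phase 2): Section 23.2 exempts any first blanking-period re-ablation, Section 3.4.2 only one done with the study system, and no failure list covers a pulmonary vein or posterior wall redo with another catheter

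*Combined protocol and SAP*

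**What the plan says.** All sections cited are in Appendix A (Phase 2) unless stated.

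- **3.4.2, Persistent AF Chronic Success.** During blanking, "recurrent arrhythmias can be managed with AADs, cardioversion or one re-ablation procedure with the FARAPULSE PFA System without constituting Persistent AF Chronic Failure". More than one re-ablation in that period is a failure, whatever the device. The section sends the reader to 23.2 for the full definition of the Blanking Period.
- **23.2, Blanking Period.** "An interval in which recurrent AF, AFL or AT, cardioversion or a first re-ablation do not constitute Treatment Failure". No device is named.
- **7.14.1, first re-ablation in blanking.** FARAPOINT may not be used for any redo. For the CTI the text reads "If repeat ablation is required for CTI-mediated flutter, any commercially available BSC RF catheter will be used. Such re-ablation using the methods and devices", and it ends by saying that re-ablation as described in 7.7.1 is not a Treatment Failure.
- **7.7.1**, the section cited there, is a data-collection list that begins "Procedural data will be collected including but not limited to". It names no ablation catheter.
- **7.7.2.5.** "The FARAWAVE Catheter is not allowed to complete any CTI lesion".
- **7.14.2, other redos.** "For a second re-ablation during the Blanking Period and for any re-ablation after the Blanking Period, any commercially available ablation catheter will be used". These are the redos that the section declares to be Treatment Failures.
- **3.4.1, index procedure.** "Both PWI and PVI must be achieved using only the FARAWAVE Catheter to be classified as a Persistent AF Acute Procedural Success".
- **23.2, Treatment Failure.** A failure needs a reason that the protocol stipulates.

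**The concern.** One primary endpoint carries two exemptions of different width. They diverge for a subject whose first blanking-period redo treats a PV or the posterior wall with a catheter outside the study system. Section 3.4.2, as worded, does not exempt that redo; 23.2 does; and no section stipulates that it is a failure.

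This bears on what the endpoint credits. At the index procedure, isolation counts only if FARAWAVE alone produced it. Under 23.2, the same sites could be re-isolated with another catheter by Day 90 and the subject could still end as a success of the study system. Two analysts starting from different sections could score that subject differently. In a single-arm, open-label trial, that choice should be fixed before outcomes are seen.

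A smaller wording gap concerns the CTI. FARAPOINT is barred from redo and FARAWAVE from CTI lesions, so a CTI-only redo done as 7.14.1 requires cannot be one performed with the study system, which is how 3.4.2 describes the exempt procedure.

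**Working it through.** **1. Scoring a first blanking-period redo under each section**

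| First redo in blanking | 3.4.2 | 23.2 | 7.14.1 | 7.14.2 failure list |
|---|---|---|---|---|
| PV or posterior wall, FARAWAVE | exempt | exempt | exempt | not listed |
| CTI only, BSC RF catheter | outside the wording | exempt | exempt on the natural reading | not listed |
| PV or posterior wall, other catheter | outside the wording | exempt | not covered (not the described devices) | not listed |

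The third row is the gap. The second needs only tidying. The footnote to 3.4.2 deals with CTI-dependent flutter after blanking and settles neither row.

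**2. The plan's own figure**

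Inputs (8.1.2.2, Table 8.1-3): expected rate 55%, performance goal 40%, one-sided alpha 0.025, 122 evaluable, 10% attrition, 136 subjects, 90% power. With the exact binomial at n = 122, the smallest count r with P(X ≥ r | 0.40) ≤ 0.025 is r = 60 (alpha 0.0248), and power at 55% is 0.916. 122 / 0.90 = 135.6, rounded up to 136. The plan's figures reproduce to within 2 points of power, and this point does not change them.

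**3. How many reclassified subjects would change the verdict**

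Section 8.1.2.3 uses a log-log pointwise lower limit on the Kaplan-Meier estimate. Without censoring, for s successes in n and p = s/n:

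- se = √[(1 − p)/(n·p)] / |ln p|
- lower limit = p^exp(1.96 × se)

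At n = 122 the planned count is 0.55 × 122 = 67.1, taken as 67:

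| s | p | se | exp(1.96 × se) | lower limit | against 40% |
|---|---|---|---|---|---|
| 67 | 54.9% | 0.1369 | 1.308 | 45.7% | pass |
| 60 | 49.2% | 0.1297 | 1.289 | 40.05% | pass |
| 59 | 48.4% | 0.1288 | 1.287 | 39.3% | fail |

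Break-even: 67 − 59 = 8 subjects, or 8/122 = 6.6 points. Each subject moves the rate by 1/122 = 0.82 points.

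At n = 258 the planned count is 0.55 × 258 = 141.9, taken as 142:

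| s | p | lower limit | against 40% |
|---|---|---|---|
| 142 | 55.0% | 48.8% | pass |
| 120 | 46.5% | 40.33% | pass |
| 119 | 46.1% | 39.95% | fail |

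Break-even: 142 − 119 = 23 subjects, or 23/258 = 8.9 points. Each subject moves the rate by 1/258 = 0.39 points.

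The documents give no rate of first redo with another catheter, so no number of affected subjects is assumed.

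**The case against.** The strongest reply is that the text already gives one answer. The failures in 3.4.2 are post-blanking events and a second blanking-period redo. It never says that a first redo with another catheter fails, it defers to 23.2 for the definition, and 23.2 requires a stipulated reason for failure. On that reading the subject is exempt and nothing conflicts. This stands as a description of the present text, but it also exposes the weakness: the device words in 3.4.2 then have no effect, and re-isolation by another catheter can be credited to the study system.

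A second reply is that the case arises only through a protocol deviation. 7.14.1 prescribes the study methods, and 3.3 specifies FARAWAVE only for a redo that counts toward safety. That is correct and is the main reason the point is minor. Deviations still have to be scored.

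Three stronger readings are tempting, and the documents do not support them.

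- **The protocol mandates an RF CTI redo that makes the subject a primary failure.** 7.14.1 names the RF catheter and then says such re-ablation is not a failure. The contrary follows only by implication from 3.4.2. The mismatch is also limited to a CTI-only redo, because a session combining FARAWAVE and RF could fit 3.4.2.
- **The safety censoring rule in 8.1.1.3, which refers to commercial catheters before the Day 90 Assessment, shows that PV redos with such catheters were foreseen.** That rule already has in-protocol cases to cover: the RF CTI redo, a second blanking-period redo, and a post-blanking redo before a late Day 90 visit.
- **Phase 1 needs the same correction.** Its wording differs in the same way, but Appendix A 4.1.1 has Phase 1 subjects analysed under the version in which they enrolled.

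The separate statistical analysis plan to which Appendix A refers (8.3.3.5, 11.2) is not in the document reviewed. It may hold a scoring rule. The two protocol definitions would still differ.

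**Conclusion.** The point holds for Phase 2 and is minor. The blanking exemption is wider in 23.2 than in 3.4.2, and no failure list covers a first PV or posterior wall redo with a catheter outside the study system. The 23.2 wording lets such a subject count as a primary success, against the FARAWAVE-only principle of 3.4.1.

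A reader might infer that the primary result is in doubt. The figures do not support that. From the planned 55%, 8 subjects at 122 evaluable, or 23 at 258, would have to be off-protocol redos that were otherwise successes. These counts assume the planned rate is observed and nobody is censored; the 258 case also assumes that every Treatment Subject is LUX-Dx monitored. An observed rate nearer the pass mark would leave less room.

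Single Procedure Treatment Success (3.5.2), defined as Treatment Success "but counting subjects with any re-ablation for AF, AFL, or AT as Treatment Failures", already gives a lower bound on the primary rate under any reading. It does not say which rate is the primary one.

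**What to change.** Amend Appendix A before outcomes are analysed:

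1. **23.2, Blanking Period:** limit the exemption to a first re-ablation performed per Section 7.14.1, meaning PV or posterior wall with FARAWAVE and CTI with a BSC RF catheter.
2. **7.14.2:** add to the failure list a first blanking-period redo of a PV or the posterior wall with any other catheter, so that the failure is stipulated.
3. **3.4.2:** replace the reference to the FARAPULSE PFA System with the words: performed per Section 7.14.1. This covers the RF CTI redo, alone or combined with FARAWAVE re-treatment.
4. **7.14.1:** correct the cross-reference from 7.7.1 to 7.7. This alone would not settle the CTI case, because 7.7.2.5 names only FARAPOINT; items 1 and 3 do that.

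Leave Phase 1 unchanged.

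**Cost.** These are wording edits, but item 2 writes an explicit failure rule into the primary endpoint, so the change needs a protocol amendment and ethics review (14.1). The primary rate may fall slightly if any such redo occurs. Sample size, catheter choice, procedures and data collection do not change.

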3.5 Additional Endpoints and Assessments

The following additional endpoints and assessments will be analyzed and reported for Phase 2 of the ADVANTAGE AF Study.

3.5.1 Additional Safety Endpoints

The following endpoints will be descriptively analyzed:

- **Primary Safety Endpoint Through Day 360 Assessment:**
Defined as the proportion of subjects with one or more device or procedure-related CSAs assessed through Day 360 (Treatment) or Day 30 (Attempt)
- **Composite Non-Serious Adverse Events:**
Defined as the proportion of subjects with one or more composite non-serious AEs otherwise as defined in **Table 3.3-2: Composite Serious Adverse Event Definitions**.
- **Related Adverse Events**
Defined as the proportion of subjects with one or more device or procedure-related AEs
- **Any Serious Adverse Event**
Defined as the proportion of subjects with one or more SAEs whether or not device or procedure-related
- **Post-Blanking Arrhythmia Hospitalizations**
Defined as the proportion of Treatment subjects with one or more physician-directed admission to an inpatient hospital facility for at least two consecutive calendar days for the primary purpose of diagnosing or treating AF, AFL or AT beginning after Day 90
- **Post-Blanking Cardioversions**
Defined as the proportion of Treatment subjects with one or more electrical cardioversions for AF, AFL or AT after Day 90
- **Coronary Spasm Events**
Defined as the proportion of subjects with CTI-mediated AFL ablation using FARAPoint PFA catheter with any of the following events 0-48 hours following procedure:
 - Angiography performed with visualization of severe ($\geq 70\%$) spasm
 - ST elevation, defined by ST elevation of 2mm in two contiguous leads and adjudicated to be a result of coronary spasm
 - Cardiac arrest adjudicated to be a result of coronary spasm.
- **Adverse Effects of Intraprocedural Administration of Nitroglycerin**
Defined as the proportion of subjects with CTI-mediated AFL ablation using FARAPoint PFA catheter with any of the following events 0-48 hours following procedure:
 - Persistent hypotension unresponsive to medical intervention
 - Respiratory distress due to acquired methemoglobinemia assessed by an arterial blood gas with co-oximetry with MetHb $> 10\%$.

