Adjustments to the nitroglycerin dosing protocol defined above are allowed per Investigator discretion based on patient condition, but the rationale for any changes to the defined workflow will be collected. Failure to administer any pre-treatment nitroglycerin will be a protocol deviation.

Vasopressors may be administered per physician discretion given that comorbidities, drug regimens, mode of anesthesia, and baseline blood pressure will vary among subjects.

200 micrograms (μ g) of phenylephrine should be administered prior to the first dose of nitroglycerin. If not administered, the rationale will be collected.

Additional vasopressor doses may be administered at the discretion of the physician depending upon the blood pressure response to nitroglycerin. Investigators may choose to administer a different vasopressor depending upon the clinical profile of the subject. All medications administered during the procedure, dose, route and timing of administration in relation to the PFA applications will be recorded.

For those subjects with a known left dominant coronary artery system, as defined by a left heart catheterization or coronary CT angiography, the above prophylactic nitroglycerin workflow is not required. The proximity of the catheter to the artery may be directly visualized in real-time via intracardiac echocardiography. Routine hemodynamic monitoring for patients undergoing sedation and cardiac ablation is recommended.

A post-procedure 12-lead ECG will be recorded following CTI ablation to assess absence of ischemia. If the post-procedure ECG shows any ischemic changes, a transthoracic echocardiographic assessment is **required** the same day as the procedure to assess if intraventricular wall motion abnormalities are observed compared to the pre-procedure echocardiographic assessment (Section 7.8).

After CTI ablation is completed, BDB will be assessed, and if necessary, additional applications may be performed until BDB is confirmed. The CTI ablation data will be documented in the CRF.

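### The nitroglycerin adverse-effect endpoint counts all FARAPOINT CTI subjects, including any who received no nitroglycerin, so its rate can be diluted or contaminated

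*Combined protocol and SAP*

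**What the plan says.** Appendix A 3.5.1 lists two additional safety endpoints specific to FARAPOINT: Coronary Spasm Events, and Adverse Effects of Intraprocedural Administration of Nitroglycerin. Both are given the same population, the "proportion of subjects with CTI-mediated AFL ablation using FARAPoint PFA catheter with any of the following events 0-48 hours following procedure". The section opens with "The following endpoints will be descriptively analyzed", so neither carries a hypothesis or performance goal.

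The nitroglycerin endpoint has two event types. One is "Persistent hypotension unresponsive to medical intervention", with no statement that nitroglycerin must be the cause. The other is respiratory distress from acquired methemoglobinemia, confirmed by blood gas.

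Appendix A 7.7.2.5 sets out who gets the drug. The general rule is "The following prophylactic workflow is required to be followed when CTI ablation is performed with the FARAPoint PFA Catheter". An exemption follows for subjects already shown by catheterization or CT angiography to be left dominant; in their case "the above prophylactic nitroglycerin workflow is not required". Investigators may also adjust the dosing with a recorded rationale, and "Failure to administer any pre-treatment nitroglycerin will be a protocol deviation". None of these provisions removes a subject from the endpoint population. The same section requires that "All medications administered during the procedure, dose, route and timing of administration in relation to the PFA applications will be recorded".

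**The concern.** The endpoint is named for an exposure, but its population is defined by something else. A rate of drug harm is normally read as the risk in people who had the drug. Here the denominator may hold exempt subjects who were given none, and subjects in whom every dose was omitted as a deviation.

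Two distortions are possible. If unexposed subjects have no qualifying events, they lower the reported rate. If an unexposed subject has refractory hypotension for another reason, it is counted as a nitroglycerin effect.

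Nitroglycerin is the protocol's stated mitigation for coronary spasm with FARAPOINT (Appendix A 1.2 and 16.6), and this is the endpoint dedicated to its tolerability. At stake is how accurately that tolerability is described. Study success does not depend on it.

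**Working it through.** **Figure to reproduce.** The plan gives no expected rate, sample size or precision for this endpoint, so there is nothing to reproduce. The only related count is the target in Appendix A 4.1.2 of an estimated 80 FARAPOINT subjects, with no upper limit. It is a rounded figure: 0.30 × 258 = 77.4.

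**Inputs.** N = 80 (Appendix A 4.1.2). The share f of FARAPOINT CTI subjects given no nitroglycerin is not in the documents. I assume 0% to 20% and show the range.

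**General relation.** Let r_e be the event rate in recipients and r_u the rate in non-recipients. The rate as defined is

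r = (1 − f) × r_e + f × r_u.

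It falls below r_e when r_u < r_e, exceeds it when r_u > r_e, and equals it when f = 0.

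**Dilution only (r_u = 0).** Recipients number 80 × (1 − f). With x events the comparison is x/80 against x/[80(1 − f)]. With zero events the one-sided 95% upper bound is 1 − 0.05^(1/n).

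| f | Recipients | 2 events: as defined / recipients | 4 events: as defined / recipients | 0 events, upper bound: as defined / recipients |
|---|---|---|---|---|
| 0% | 80 | 2.5% / 2.5% | 5.0% / 5.0% | 3.7% / 3.7% |
| 5% | 76 | 2.5% / 2.6% | 5.0% / 5.3% | 3.7% / 3.9% |
| 10% | 72 | 2.5% / 2.8% | 5.0% / 5.6% | 3.7% / 4.1% |
| 15% | 68 | 2.5% / 2.9% | 5.0% / 5.9% | 3.7% / 4.3% |
| 20% | 64 | 2.5% / 3.1% | 5.0% / 6.3% | 3.7% / 4.6% |

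**Contamination.** Take f = 10%, so 72 recipients and 8 non-recipients. Suppose two events occur in recipients and one hypotension event in a non-recipient. The rate as defined is 3/80 = 3.75%, against 2/72 = 2.8% among recipients. The error now runs the other way.

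**Against sampling error.** The exact 95% interval is 0.3–8.7% for 2/80 and 0.4–10.8% for 2/64. The shift from 2.5% to at most 3.1% is small beside either.

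**Is it repaired elsewhere?** The subgroup list (Appendix A 8.3.4) and covariate list (8.3.7) concern the primary endpoints and include neither nitroglycerin receipt nor coronary dominance. Nothing in Appendix A section 8 restricts this endpoint to recipients.

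**The case against.** The strongest reply is that the unexposed group may hardly exist. The exemption waives the workflow without forbidding the drug. It covers only subjects whose left dominance is already known, and Appendix A 7.5 collects coronary anatomy only where an earlier catheterization or CT angiogram supplies it. The deviation rule concerns pre-treatment, and a subject who missed that may still have received boluses during ablation. All of this stands. It means exposure must be judged by actual administration, not by dominance or deviation status, and that f = 0 belongs in the range.

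A reader might infer that the rate is understated by construction. The documents do not support that: f may be zero, and hypotension in a non-recipient can push the rate up.

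A reader might also infer that the Coronary Spasm rate is wrong because it pools subjects with and without prophylaxis. It is not. The exemption is part of the protocol, so the pooled rate is a valid rate for FARAPOINT as used. Subjects without prophylaxis would be few and largely selected by anatomy; with zero events in 4 to 16 subjects (5–20% of 80), the two-sided exact 95% upper limit runs from 60% down to 21%. Such a split cannot show what prophylaxis does.

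Nor are these two endpoints the only Phase 2 evidence on FARAPOINT risk. The primary safety endpoint includes myocardial infarction and PFA-related cardiovascular events, it is examined by CTI ablation versus none (8.3.4), and ischemic findings are separately reportable (17.1 to 17.3).

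Finally, the separate Phase 2 SAP to which Appendix A refers is not in the document reviewed and may define an exposed-only table. That cannot be judged here, and the protocol wording would still need to agree with it.

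**Conclusion.** The point holds as a mismatch between the endpoint's name and its population. As written, the rate is not confined to subjects who received nitroglycerin and can be diluted or contaminated by those who did not. Neither the direction nor the size can be fixed from the documents.

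Under an assumed unexposed share of 0–20% of 80, with all events in recipients, two events read as 2.5% instead of 2.5–3.1%, and the zero-event one-sided 95% upper bound reads as 3.7% instead of 3.7–4.6%. With no unexposed subjects there is no effect.

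The consequence is limited to one descriptive safety rate. The primary endpoints, sample size and type I error are untouched, and the Coronary Spasm population needs no correction.

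**What to change.** In Appendix A 3.5.1, and in the Phase 2 SAP if it repeats the definition, define the nitroglycerin endpoint among subjects with FARAPOINT CTI ablation who received at least one intraprocedural nitroglycerin dose. Report events, denominator and an exact confidence interval, and state how many FARAPOINT CTI subjects received none. Settle this before analysis, so that the denominator is not chosen after an event is seen.

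Keep Coronary Spasm Events in all FARAPOINT CTI subjects. A tabulation by nitroglycerin received (yes/no) may be added as an optional descriptive supplement, labelled as not comparing the effect of prophylaxis.

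The cost is one definition and one denominator. The procedural medication record required by 7.7.2.5 already holds the data, so no new collection or change in clinical management is needed. The reported rate may come out slightly higher or lower than under the current definition.
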